Power considerations focus on our primary hypotheses, which examine intervention effects on two primary outcomes, drinking days per week and average drinks per drinking day, at 3 months follow-up. For our principal analyses we will separately examine effects on these outcomes at 3 months through analysis of covariance, controlling for baseline levels of the outcome variable. Reported effects of brief intervention vary in the literature.

For instance, a meta-analysis by Moyer et al. found an effect size for alcohol consumption in non-treatment-seeking samples of 0.67 for drinks per day at three months, but it quickly drops to 0.14 at six months, and 0.24 at 12 months.⁹⁵ On the other hand, Bien et al. reported an average effect size of 0.64 at 12 months for the reduction in drinks per month, but it varied in studies they reviewed from 0.27 to over 1.0.¹⁷ More to the point for our study, Riper et al.⁹⁶ conducted a meta-analysis of web-based brief interventions and reported a medium effect size ($d=0.44$). There are little data to suggest that those with alcohol use disorders derive more or less benefit from brief intervention.³³ However, VA clinical guidelines suggest that people with alcohol use disorders need to be referred to specialty treatment, implying that they might not be expected to benefit solely from brief intervention. With these prior studies in mind, and with the explicit design of this study as an initial, single-site RCT to assess the potential effectiveness of the Relational Agent Intervention on frequency and quantity of alcohol use among Veterans, we have powered the trial for the detection of a large effect size, as defined by Cohen.⁹⁷

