We begin our sample size estimation with the observation that 5,571 underwent AUD-C screening in our study setting during fiscal year 2010. We estimate that $1.25 * 5,571 = 6,963$ will be screened during the **15-month** study enrollment period. National samples indicate that about 20% of Veterans screened receive a positive score on the AUD-C,²⁶ which would be consistent with the estimated prevalence in the larger population. Therefore, $6,963 * 0.2 = 1,393$ Veterans will be potentially eligible. Because of clinic workflow and research assistant availability, we anticipate approaching approximately **500** of these Veterans. Based on [name] pilot study of a Relational Agent to screen for alcohol problems in primary care (described above, Section 4.a.1) and the two recently completed pilot studies of the Relational Agent in the Primary Care Clinic of VA Boston, we estimate that **36% of the 500** Veterans approached, or **180** Veterans, will agree to participate. We estimate that these **180** Veterans will be distributed in a 2:1 ratio as those with alcohol use disorders ($N=120$) and those with risky drinking ($N=60$), based on studies in VA.

Rates of attrition, or loss-to-follow-up, in prior studies of brief intervention for alcohol problems have typically ranged from 10% to 30%. Based on our familiarity with following up study participants in alcohol and substance abuse interventions, and particularly noting our use of financial compensation for participation, we anticipate that our loss-to-follow-up will be on the lower end of this range. However, in the table below we show power estimates for three possible rates of loss to follow-up: 20%, 25% and 30%. Table 5 shows estimated power to detect a **medium (Cohen's) effect size**, at an alpha level of 0.05, given the three possible rates of loss-to-follow-up.

Power estimates for a range of loss-to-follow-up rates

% Loss-to-Follow-Up	Experimental Group	Alcohol Use Disorders (N)	Risky Drinking (N)	Total (N)	Power
20%	TAU	48	24	72	0.84
	TAU+RAI	48	24	72	
25%	TAU	45	22.5	68	0.82
	TAU+RAI	45	22.5	68	
30%	TAU	42	21	63	0.78
	TAU+RAI	42	21	63	

Note: TAU=Treatment as Usual; RAI=Relational Agent Intervention.

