Thus, for our primary outcome, we estimate that we will have more than 80% power to detect a medium effect of the intervention with loss-to-follow-up rates approaching 30%. We will monitor loss-to-follow-up closely and, if we discover that the attrition rate is exceeding 30%, we will increase our sample size to account for the loss-to-follow-up.

We will recruit a total of **180** Veterans from PCC, with approximately **60** participants in the Risky Drinking Group and **120** participants in the Alcohol Use Disorders Group. Accounting for 20-30% loss to follow up we expect that at least **126 to 144** Veterans will complete the 3-month follow-up.

Specific Aim 3: Examine in-depth Veterans' experience with the Relational Agent Intervention.

Because this Aim is exploratory in nature, there are no associated hypotheses. Following the RCT, we will conduct a formative evaluation (Aim 3), with in-depth interviews, to characterize the elements of the Relational Agent Intervention that Veterans prefer, and the features that emerge as most effective and those that seem extraneous or even counter-productive.

Rationale for formative evaluation

Formative evaluation will inform future evaluation and implementation efforts, specifically in the area of Relational Agents for alcohol problems and more generically for interventions using health information technology to engage Veterans in their care in the primary care setting. Formative evaluation is valuable in the context of an intervention that results in quantitative improvement of outcomes because it can yield information regarding those characteristics of the intervention that seemed most useful and effective from the perspective of the study participants. Perhaps more importantly, formative evaluation is crucial in the context of an intervention that does not result in quantitative improvement in the target outcome (i.e., in the setting of a "negative study"), because it can identify the factors that may have prevented an otherwise-potent intervention from achieving the intended outcome.

In-depth Interviews

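### The plan says the trial is powered for a large effect, but its power table is for a medium one (d of about 0.5), and power at 30% loss is 0.78, not above 0.80

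*Combined protocol and SAP*

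**What the plan says.** All the relevant text is in the combined protocol and SAP, under Sample Size and Power Considerations.

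- **Target effect in the narrative.** After reviewing published effects of brief intervention, the section says "we have powered the trial for the detection of a large effect size", citing Cohen's definition.
- **Target effect in the table.** The power table is introduced as showing "estimated power to detect a medium (Cohen's) effect size", "at an alpha level of 0.05". No number is attached to medium, and the sidedness of the test is not stated.
- **The table.** The plan says "in the table below we show power estimates for three possible rates of loss to follow-up: 20%, 25% and 30" per cent. The rows have 72, 68 and 63 completers per arm, with power 0.84, 0.82 and 0.78.
- **The conclusion.** The text after the table says "we estimate that we will have more than 80% power to detect a medium effect of the intervention with loss-to-follow-up rates approaching 30" per cent. It adds that the sample size will be raised if attrition exceeds 30%.
- **Evidence.** Among the cited sources is a group that "conducted a meta-analysis of web-based brief interventions and reported a medium effect size", with d = 0.44. The plan introduces this source as the one closest to its own intervention.
- **Analysis.** The primary analysis is ANCOVA with the baseline value of the outcome as covariate. No baseline to follow-up correlation is given.

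**The concern.** A design has one target effect, and this section names two. A reader who stops at the narrative will think that the trial can reliably detect only a large effect. A reader who goes on to the table will think that it can detect a medium one. The difference matters most after a null result, which the plan itself considers when it justifies the Aim 3 interviews. What such a result rules out depends on the effect that the trial was sized for.

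The closing sentence adds a smaller problem. It rounds the table upwards by describing only the loss rates short of 30%, and so passes over the one row that falls under 80%. The sample size safeguard acts only above 30%, when by the plan's own figures power is already a little under the stated level.

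**Working it through.** **Inputs from the documents:** 180 randomised, which the table implies is 90 per arm; loss L of 20%, 25% and 30%; alpha 0.05; printed power 0.84, 0.82 and 0.78.

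**Assumptions:** a two-sided test; medium taken as d = 0.5 and large as d = 0.8, since the documents print neither number; and, to begin with, no gain from the baseline covariate.

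**Step 1: reproduce the table.** Completers per arm are n = 90 × (1 − L), which gives 72, 67.5 (printed as 68) and 63. Power is the probability that a noncentral t variable with 2n − 2 degrees of freedom and noncentrality d × √(n/2) exceeds the two-sided 5% critical value in absolute size. At n = 72 and d = 0.5 the noncentrality is 0.5 × √36 = 3.00. At n = 63 it is 0.5 × √31.5 = 2.81.

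| Loss | n per arm | Printed | d = 0.5 | d = 0.8 | d = 0.44 |
|---|---|---|---|---|---|
| 20% | 72 | 0.84 | 0.846 | 0.9975 | 0.746 |
| 25% | 68 (67.5) | 0.82 | 0.825 (0.822) | 0.996 | 0.722 (0.718) |
| 30% | 63 | 0.78 | 0.795 | 0.994 | 0.688 |

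The d = 0.5 column agrees with the printed values to within 2 points in every row. An F test with f = 0.25 gives the same results. Other settings do not fit: one-sided 0.05 gives 0.91, 0.90 and 0.87, and two-sided 0.025 gives 0.77, 0.74 and 0.70. The d = 0.8 column is nowhere near the table, so the table cannot be for a large effect.

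The table alone cannot separate d = 0.5 without a covariate from a smaller d with a compensating correlation. For example, d = 0.44 with r = √(1 − 0.44²/0.5²) = √0.2256 = 0.475 gives the same effective effect. But the plan names Cohen's medium and mentions no correlation, so the first reading is the natural one.

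**Step 2: where power crosses 80% at d = 0.5.** By the t calculation, 64 per arm gives 0.8015 and 63 gives 0.795. So 128 completers are needed, and the tolerable loss is 1 − 128/180 = 28.9%. Linear interpolation of the printed table gives 25 + 5 × (0.82 − 0.80)/(0.82 − 0.78) = 27.5%. Both are below the 30% that triggers a sample size increase.

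**Step 3: sensitivity at the cited d = 0.44.** Without covariate gain, power is 0.75, 0.72 and 0.69. With ANCOVA the effective effect is d/√(1 − r²), where r is the baseline to follow-up correlation. At r = 0.5 (assumed) this is 0.44/√0.75 = 0.508, and power is 0.857, 0.834 and 0.808. The smallest r that brings power to 80% is about 0.36 at 20% loss, 0.43 at 25% and 0.49 at 30%.

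**The case against.** The strongest reply is that nothing is hidden and little is at stake. The row with 0.78 stands directly above the sentence in question, and a rate approaching 30% is not 30%. On exact calculation power stays above 0.80 until about 29% loss. At 30% it is 0.795 by the t-test and 0.801 by the normal approximation. The plan also expects attrition towards the low end of 10% to 30%. At 10% loss (81 per arm) power at d = 0.5 is 0.886, and at 20% it is 0.846. All of this stands. A reader might infer that the sentence flatly contradicts the table; the documents do not support that. The sentence is imprecise, by about one percentage point of loss on exact calculation (28.9% against 30%) or 2.5 points on the printed table.

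A reader might also infer that the trial falls short of its own target because power at d = 0.44 is below 80%. The documents do not support that either. The conclusion rests on the table, which is for Cohen's medium effect, and the plan never claims 80% power at 0.44. The same paragraph cites 0.67 for drinks per day at three months, which is this trial's follow-up time, along with lower values at later times. Choosing a target within that range is a design judgement. The unadjusted figures also leave out the planned ANCOVA, which may recover the power. At d = 0.5 and 30% loss, a correlation of only 0.2 gives 0.811.

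The reply does not remove the conflict between large and medium. The table and conclusion agree with each other, so the conflict changes neither the sample size nor the analysis. It still leaves a design property misstated.

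**Conclusion.** The point holds as a correction to the stated design. The narrative's large effect is inconsistent with the table and conclusion. The table fits d of about 0.5, two-sided 0.05, with no covariate gain: 0.846, 0.825 and 0.795 against the printed 0.84, 0.82 and 0.78. At d = 0.8 every row would be 0.99 or more. This rests on the usual values for Cohen's labels and on a two-sided test, neither of which the documents print.

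The summary of more than 80% power is loose but not false. It fails at 30% loss by 2 points on the plan's table and by half a point on exact calculation, and the attrition trigger acts only beyond that level.

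The d = 0.44 figures belong in the plan as a conditional sensitivity analysis. Whether power there is below or above 80% depends on a correlation that the documents do not give, so no finding of an underpowered trial follows.

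**What to change.** In Sample Size and Power Considerations:

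1. Replace *large* with *medium (d = 0.5)* in the narrative, and print the same number with the power table. State that the test is two-sided and that no gain from the baseline covariate is assumed, if the sponsor confirms both.
2. Restate the conclusion: power for d = 0.5 exceeds 80% at up to about 25% loss (0.82) and is 0.78 at 30% loss. Note that power is therefore slightly under 80% by the time the rule for increasing the sample size applies.
3. Add one sensitivity line: at the cited d = 0.44, unadjusted power is 0.75, 0.72 and 0.69 at 20%, 25% and 30% loss. The planned ANCOVA reaches 80% if the baseline to follow-up correlation is at least about 0.36, 0.43 and 0.49 respectively. Give any correlation that the team is willing to assume, with its source.

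The cost is a few sentences. No patients are added and the analysis does not change. The stated power becomes slightly less favourable.

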We will perform a content analysis of the transcribed in-depth interviews, incorporating the principles of the immersion-crystallization method. This qualitative approach consists of repeated cycles of immersion into the collected data with subsequent emergence, after reflection, of an intuitive crystallization of the dominant themes.⁶³ [name] and research staff will independently listen to selected interview tapes, read all transcripts and write analytic notes for each observation or interview. They will meet regularly to discuss each transcript and will compile detailed notes of each meeting to document emerging themes and maintain a permanent record of the analysis. This process will allow thorough immersion in the data within the context of each interview in its entirety. We will then compare the data from the transcript under discussion with the data from other analyzed transcripts. Through this process, we will identify salient themes that crystallize from the interviews. [name] and the research staff will each then code the transcripts and observation guides based on these themes, as well as broad content areas suggested by overall goals of the sessions. [name] and the research staff will meet regularly with [name], [name] and other members of the team to review the emerging themes and coding strategies. We will continue analysis until no new major themes emerge.

Examples from the transcribed interviews will be used to illustrate the findings that emerge. We will address recognized criteria for qualitative research: credibility, fittingness, auditability, and confirmability. We will establish credibility by including the research associate in discussions with the study team to determine the

concordance between coded themes and the real-time research associates' experiences. In addition, having multiple individuals read and code each of the transcripts will enhance credibility. We will assess fittingness through line-by-line analysis of the transcripts and by linking extensive verbatim examples to each theme.

Through iterative discussions among the study team, these qualitative findings will be used to characterize the degree to which the Relational Agent Intervention considerations for future implementation of the intervention.

(5) Human Subjects

Aims 2 and 3: Risk to Subjects

The overall goal of this project is to develop a Relational Agent Intervention to improve brief intervention for alcohol problems in primary care, and compare its effectiveness with treatment as usual. Aim 1 of this study has already been approved. Aim 2 is quantitative: an initial RCT to compare the effect of an intervention on Veterans' consumption of alcohol to that of standard treatment in primary care. Human subjects' risks and protections will be addressed for Aims 2 and 3 here. Benefits, importance of knowledge to be gained, the data safety monitoring plan and inclusion of women, children and minorities are the same for all parts of the project, and will be copied from the Aim 1 approval for the convenience of the reviewers.

Human Subjects Involvement and Characteristics

For Aim 2, 180 primary care patients who are attending a primary care appointment at VA Boston will be recruited into this study. Both men and women will be recruited. Veterans identified by clinic staff as screening positive on the AUD-C for alcohol use (score of ≥ 5) will be eligible for screening. As detailed above, Veterans will be eligible if drinking above CDC guidelines in the past 30 days. They will be ineligible if they do not have a stable telephone number and mailing address for the next 6 months, or if they have participated in substance abuse treatment in the past 30 days.

Participants will participate in research interviews at baseline (right after screening) and 3 months. Participants randomized to the experimental arm will also come in at one month for a second visit with the Relational Agent.

For Aim 3, 20 of the RCT participants in the experimental arm will be invited to participate after their 3 month interview is complete. We will use purposive sampling to identify potential participants allocated to the Treatment as Usual plus Relational Agent Intervention group, recruiting approximately equal numbers of Veterans who had a reduction in alcohol use and those who had no reduction. We will recruit a total of 20 Veterans.

Sources of Materials

Data for Aim2, the RCT, will be obtained from two sources. Data will be obtained specifically for research from questionnaires, from the computer program providing screening and brief intervention, and from participant interviews. Data will also be obtained from CPRS to record whether the expected screening and brief intervention occurred in the "Treatment as Usual" arm of the study, and to gather information on other psychiatric problems that may affect the outcomes of the study.

Veterans will be asked questions to assess their levels of health literacy, computer literacy, and attitudes toward the Intervention, as well as drinking problems and general descriptors (e.g., age, gender, previous substance abuse treatment). We will also have information about process variables from the participants who use the Relational Agent program (e.g., pros and cons of drinking, confidence level to change, etc.)we will obtain that information from participants.

Data for Aim 3, the formative interviews, will be obtained via in-depth interviews with participants about their reactions to and assessment of the Relational Agent intervention.

Potential Risks

The research risk is minimal and involves additional questions and the administration of a computerized screening, brief intervention, and referral to treatment for alcohol problems (commonly referred to as SBIRT). Since each group receives treatment as usual, and primary care clinicians are supposed to provide a brief intervention and referral if appropriate for patients who screen positive on the AUDIT, the research-related SBIRT is in addition to usual care.

Clinic staff administer the AUD-C once a year to all Veterans. If a Veteran scores above the cutoff, clinic staff will inform the Veteran about the study and ask them to sign the "permission to contact" form if they are interested. This form will be passed on to the Research Assistant, who will meet with the Veteran to conduct the screening. The RA will briefly explain what the study is about and ask if the Veteran will have a stable phone number and address for the next 6 months. If the answer is yes, the research assistant will administer the Quick Drinking Screen (quantity and frequency of drinking in the past 30 days). If the Veteran is drinking above CDC guidelines, additional screening questions will be administered. If the Veteran is eligible, the consent form will be read to the participant. The RA will stop after each page or each section of the ICF and ask if the veteran understands or has any questions. Once the ICF has been signed, the RA will ask about substance Abuse treatment in the last month. If the veteran has not had treatment in the last month, the RA administer baseline questionnaires, randomize the participant, and inform the participant of their assignment, and an appointment for the 3 month follow up will be scheduled. If the Veteran has been assigned to the Relational Agent, the RA will set up the program, explain what the veteran needs to do, then let the veteran use the program. When the veteran finishes the program, the one month appointment for the second session will be scheduled if appropriate.

Protection against Risk

As described above, the potential risks to subjects in this study are of low likelihood and generally not serious. Nevertheless, we have given these risks careful consideration and have developed a plan to ensure that research subjects are protected against them. With respect to ensuring confidentiality and data security,

we will take the following precautions. We will only collect identifiable data when absolutely necessary and scientifically justified. All data will be stored on VA-encrypted laptops and on VA servers behind the VA firewall. Data transmissions between study staff will be minimized, but when necessary, will meet or exceed all standards for encryption and security that are in place for the electronic transmission of Veterans' clinical information, with which the Principal Investigator is familiar. The master list will be stored separately from the coded data.

This project is unique in that it brings together three high priority areas for VA; improving mental and behavioral health interventions, specifically, brief alcohol interventions in primary care; transforming care through the use of healthcare informatics, specifically, the Relational Agent; and reducing health care disparities, through the use of an eHealth tool that has few barriers to use by Veterans who may have poor health and computer literacy. If ultimately proven effective, the use of this eHealth tool for multiple behavioral issues can be integrated into the interface between primary care and behavioral health, and can fit well into the model of Patient Aligned Care Teams.

The knowledge to be gained from this study will be significant in addressing three high priority areas at once, and point to the pathway for using patient-facing technology to meet the 21st century requirements for all of our Veterans to be more involved in their own care. It will provide information on integrating eHealth tools into primary care as well as the effectiveness of this tool, at least for unhealthy alcohol use. The potential knowledge to be gained from this project outweighs the minimal risks to participants.
